#### 15.1.1 Conservative (upper bound) inference and sensitivity analysis for the Cox model correlates of risk analysis

While the above nonparametric approach is considered to be the best scientific approach because it takes the greatest care to avoid the correctness of inferences depending on parametric modeling assumptions that cannot be fully verified, we also apply the same Cox modeling approach described in Section 12.3.3, augmented with a sensitivity analysis, which harmonizes with the CoR analysis, and sensitivity analysis is generally warranted when a no unmeasured confounders assumption is made. The sensitivity analysis quantifies the rigor of evidence for a controlled VE CoP after accounting for potential bias from unmeasured confounding.

Gilbert et al. (2020a) details the sensitivity analysis approach, which was applied to the CYD14 and CYD15 dengue phase 3 data sets (Moodie et al., 2018); we plan to apply it in the same way to the COVID-19 data sets (as the structure of the problem is the same). We summarize here the essential details needed for application to the COVID-19 data sets.

We define S to be a controlled risk CoP if P(Y(1,s) = 1) is monotone nonincreasing in s with P(Y(1,s) = 1) > P(Y(1,s') = 1) for at least some s < s', where point and 95% confidence interval estimates of P(Y(1,s) = 1) versus s, with built in robustness to unmeasured confounding, describe the strength of the CoP in terms of the amount and nature of decrease. Suppose the CoR analysis based on the Cox model is conducted as described in Section 12.3.3.

Let marginalized conditional risk

$$r_M(s) = risk_1(t_F|s)$$

and controlled risk

$$r_C(s) = P(Y(1, s) = 1).$$

Given that CoR analysis is based on observational data — the biomarker value is not randomly assigned — a central concern is that unmeasured or uncontrolled confounding of the association between S and Y could render  $r_M(s) \neq r_C(s)$ , biasing estimates of the controlled risk curve  $r_C(s)$  and of controlled risk ratios of interest

$$RR_C(s_1, s_2) = r_C(s_2)/r_C(s_1)$$

Because we can never be certain that confounding is adequately adjusted for, sensitivity analysis is warranted, as considered in extensive literature see, e.g., VanderWeele and Ding (2017) and references therein. Sensitivity analysis is useful to evaluate how strong unmeasured confounding would have to be to explain away an observed causal association, that is, to determine the strength of association of an unmeasured confounder between S and Y needed for the observed exposure-outcome association to not be causal,  $r_M(s) \neq$  $r_C(s)$ . We follow the recommendation of VanderWeele and Ding (2017) to report the E-value as a summary measure of the evidence of causality, or, in our application, evidence of whether S is a controlled risk CoP based on variation in the controlled risk curve. We also include other closely related measures of sensitivity.

The E-value is the minimum strength of association, on the risk ratio scale, that an unmeasured confounder would need to have with both the exposure (S) and the outcome (Y) in order to fully explain away a specific observed exposure–outcome association, conditional on the measured covariates [VanderWeele and Ding (2017); VanderWeele and Mathur (2020)]. If, as in CoP analyses, the estimated marginalized risk ratio  $\widehat{RR}_M(s_1, s_2) = \widehat{r}_M(s_2)/\widehat{r}_M(s_1)$ for  $s_1 < s_2$  is less than one, then the E-value for  $\widehat{RR}_M(s_1, s_2)$  is calculated as

$$e_{RR}(s_1, s_2) = \frac{1 + \sqrt{1 - \widehat{RR}_M(s_1, s_2)}}{\widehat{RR}_M(s_1, s_2)} .$$
(19)

We include the argument  $(s_1, s_2)$  in the notation, with  $s_1 < s_2$  by convention, to be clear that the E-value depends on specification of two specific markerlevel subgroups.

To illustrate the interpretation of an E-value, suppose S is binary and regression analysis yields an estimate  $\widehat{RR}_M(0,1) = \widehat{r}_M(1)/\widehat{r}_M(0) = 0.40$  with 95% confidence interval (CI) (0.14, 0.78). An E-value e(0,1) of 4.4 means that a marginalized risk ratio  $RR_M(0, 1)$  at the observed value 0.40 could be explained away (i.e.,  $RR_C(0, 1) = 1.0$ ) by an unmeasured confounder associated with both the exposure and the outcome by a marginalized risk ratio of 4.4-fold each, after accounting for the vector X of measured confounders, but that weaker confounding could not do so.

In addition, we follow the recommendation of VanderWeele and Ding (2017) to also report the E-value  $e_{UL}(s_1, s_2)$  for the upper limit  $\widehat{UL}(s_1, s_2)$  of the 95% CI for the observed marginalized risk ratio  $\widehat{RR}_M(s_1, s_2)$ , computed as 1 if  $\widehat{UL}(s_1, s_2) \geq 1$  and, otherwise, as

$$\frac{1+\sqrt{1-\widehat{UL}(s_1,s_2)}}{\widehat{UL}(s_1,s_2)}$$

,

which in the example equals  $e_{UL}(0, 1) = 1.88$ . This E-value for the upper limit indicates, for given  $s_1 < s_2$ , the strength of unmeasured confounding at which statistical significance of the inference that  $RR_C(s_1, s_2) < 1$  would be lost. The two E-values above are useful for judging how confident we can be that an immunologic biomarker is a controlled risk CoP, with E-values near one suggesting weak support and evidence increasing with greater E-values.

 $RR_C(s_1, s_2) = (1 - CVE(s_2))/(1 - CVE(s_1))$ , evidence for  $RR_C(s_1, s_2) < 1$  is equivalently evidence for  $CVE(s_1) < CVE(s_2)$ . Thus in a placebo-controlled trial  $RR_C(s_1, s_2)$  can be interpreted as the multiplicative degree of superior vaccine efficacy caused by marker level  $s_2$  vs. marker level  $s_1$ , and E-values equivalently quantify evidence for whether  $CVE(s_1)$  differs from  $CVE(s_2)$ .

It is also useful to provide conservative estimates of controlled risk ratios and of the controlled risk curve, accounting for unmeasured confounding. We approach these tasks based on the sensitivity analysis, or bias analysis, approach of Ding and VanderWeele (2016). We give their main result and refer readers to the paper for details. We begin by defining two (possibly context-specific) fixed sensitivity parameters. First, we set  $RR_{UD}(s_1, s_2)$  to be the maximum risk ratio for the outcome Y comparing any two categories of the unmeasured confounders U, within either exposure group  $S = s_1$  or  $S = s_2$ , conditional on the vector X of observed covariates. Second, we set  $RR_{EU}(s_1, s_2)$  to be the maximum risk ratio for any specific level of the unmeasured confounder U comparing individuals with  $S = s_1$  to those with  $S = s_2$ , with adjustment already made for the measured covariate vector X. Thus,  $RR_{UD}(s_1, s_2)$  quantifies the importance of the unmeasured confounder U for the outcome, and  $RR_{EU}(s_1, s_2)$  quantifies how imbalanced the exposure/marker subgroups  $S = s_1$  and  $S = s_2$  are in the unmeasured confounder U. The values  $RR_{UD}(s_1, s_2)$  and  $RR_{EU}(s_1, s_2)$  are always specified as greater than or equal to one. We suppose that  $RR_M(s_1, s_2) < 1$  for the fixed values  $s_1 < s_2$  — this is the case of interest for immune correlates.

Define the bias factor

$$B(s_1, s_2) = \frac{RR_{UD}(s_1, s_2)RR_{EU}(s_1, s_2)}{RR_{UD}(s_1, s_2) + RR_{EU}(s_1, s_2) - 1}$$

for  $s_1 \leq s_2$ , and define  $RR_M^U(s_1, s_2)$  the same way as  $RR_M(s_1, s_2)$ , except marginalizing over the joint distribution of X and U. Then,  $RR_M^U(s_1, s_2) \leq$  $RR_M(s_1, s_2) \times B(s_1, s_2)$ , where  $RR_M^U(s_1, s_2) = E\{r(s_2, X^*)\}/E\{r(s_1, X^*)\}$ with  $X^* = (X, U)$  and r conditional risk defined near equation (??).Ding and VanderWeele (2016)

Translating this result to our problem context, under the positivity asymption, we have that  $RR_M^U(s_1, s_2) = RR_C(s_1, s_2)$  and so, it follows that

$$RR_C(s_1, s_2) \le RR_M(s_1, s_2) \times B(s_1, s_2) .$$
(20)

This inequality states that the causal risk ratio is bounded above by the marginalized risk ratio multiplied by the bias factor. It follows that a conservative (upper bound) estimate of  $RR_C(s_1, s_2)$  is obtained as  $\widehat{RR}_M(s_1, s_2) \times B(s_1, s_2)$ , and a conservative 95% CI is obtained by multiplying each confidence limit for  $RR_M(s_1, s_2)$  by  $B(s_1, s_2)$ . These estimates for  $RR_C(s_1, s_2)$  account for the presumed-maximum plausible amount of deviation from the no unmeasured confounders assumption specified by  $RR_{UD}(s_1, s_2)$  and  $RR_{EU}(s_1, s_2)$ . An appealing feature of this approach is that the bound (20) holds without making any assumption about the confounder vector X or the unmeasured confounder U.

The above approach does not directly provide a conservative estimate of the controlled risk curve  $r_C(s)$ , because additional information is needed for absolute versus relative risk estimation. To provide conservative inference for  $r_C(s)$ , we next select a central value  $s^{cent}$  of S such that  $\hat{r}_M(s^{cent})$  matches the observed overall risk,  $\hat{P}(Y = 1|A = 1)$ . This value is a 'central' marker value at which the observed marginalized risk equals the observed overall risk. Next, we 'anchor' the analysis by assuming  $r_C(s^{cent}) = r_M(s^{cent})$ , where picking the central value  $s^{cent}$  makes this plausible to be at least approximately true. Under this assumption, the bound (20) implies the bounds

$$r_C(s) \leq r_M(s)B(s^{cent}, s) \text{ if } s \geq s^{cent}$$
 (21)

$$r_C(s) \ge r_M(s) \frac{1}{B(s, s^{cent})}$$
 if  $s < s^{cent}$ . (22)

Therefore, after specifying  $B(s^{cent}, s)$  and  $B(s^{cent}, s)$  for all s, we conservatively estimate  $r_c(s)$  by plugging  $\hat{r}_M(s)$  into the formulas (21) and (22). Because  $B(s_1, s_2)$  is always greater than one for  $s_1 < s_2$ , formula (21) pulls the observed risk  $\hat{r}_M(s)$  upwards for subgroups with high biomarker values, and formula (22) pulls the observed risk  $\hat{r}_M(s)$  downwards for subgroups with low biomarker values. This makes the estimate of the controlled risk curve flatter, closer to the null curve, as desired for a sensitivity/robustness analysis.

To specify  $B(s_1, s_2)$ , we note that it should have greater magnitude for a greater distance of  $s_1$  from  $s_2$ , as determined by specifying  $RR_{UD}(s_1, s_2)$  and  $RR_{EU}(s_1, s_2)$  increasing with  $s_2 - s_1$  (for  $s_1 \leq s_2$ ). We consider one specific approach, which sets  $RR_{UD}(s_1, s_2) = RR_{EU}(s_1, s_2)$  to the common value  $RR_U(s_1, s_2)$  that is specified log-linearly:  $\log RR_U(s_1, s_2) = \gamma(s_2 - s_1)$  for  $s_1 \leq s_2$ . Then, for a user-selected pair of values  $s_1 = s_1^{fix}$  and  $s_2 = s_2^{fix}$  with  $s_1^{fix} < s_2^{fix}$ , we set a sensitivity parameter  $RR_U(s_1^{fix}, s_2^{fix})$  to some value above one. It follows that

$$\log RR_U(s_1, s_2) = \left(\frac{s_2 - s_1}{s_2^{fix} - s_1^{fix}}\right) \log RR_U(s_1^{fix}, s_2^{fix}), \quad s_1 \le s_2.$$

We anchor the sieve analysis by setting  $s_1 = s_1^{fix}$  at the 15th percentile of the

Day 57 antibody marker and  $s_2 = s_2^{fix}$  at the 85th percentile of the Day 57 antibody marker.

The sensitivity analysis is done for each of the two Cox model CoR analyses described in Section 12.3.3, first for tertiles of the Day 57 marker and second for the quantitative marker. For the former, E-values are reported for both the point estimate and the upper 95% confidence limit for  $RR_C(0, 1)$ , where category 1 is the upper tertile, category 0 is the lower tertile, and the intermediate middle tertile subgroup of vaccine recipients is excluded from the analysis. In addition, setting  $RR_{UD}(0,1) = RR_{EU}(0,1) = 2$ , such that B(0,1) = 4/3, we report conservative estimation and inference on the causal risk ratio  $RR_C(0,1)$  and equivalently on the ratio of controlled vaccine efficacy curves (1 - CVE(1))/(1 - CVE(0)).

Next we repeat the analysis treating S as a quantitative variable, where  $P(T \leq t | S = s, X, A = 1)$  is again estimated by two-phase Cox partial likelihood regression and now  $RR_M(s_1, s_2)$  is the marginalized risk ratio between  $s_1$  and  $s_2$ . We will plot point and 95% confidence interval estimates of the observed marginalized risk and controlled risk curves, for the latter using the sensitivity analysis described in Section 15.1.1.

For validity the method requires the positivity assumption, and thus the method will only be applied if the data are reasonably supportive of the positivity assumption. To check positivity, we study the antibody marker distribution in vaccine recipients within each subgroup of the covariates X that are adjusted for. For the tertiles analysis we require evidence that within each subgroup some vaccine recipients have lower tertile responses and some vaccine recipients have upper tertile responses. For the quantitative S analysis, we look for evidence that S varies over its full range within each level of the potential confounders that are adjusted for.

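### Section 15.1.1 multiplies both confidence limits by the bias factor and calls the result a conservative 95% CI for the causal risk ratio, but only the upper limit is conservative

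*Combined protocol and SAP*

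**What the plan says.** Section 15.1.1 defines B from two sensitivity parameters and arrives at inequality (20), RR_C ≤ RR_M × B. It reads this correctly: "This inequality states that the causal risk ratio is bounded above by the marginalized risk ratio multiplied by the bias factor". It then states that "a conservative 95% CI is obtained by multiplying each confidence limit for" RR_M by B. In the tertile analysis both parameters are set to 2, "such that B(0,1) = 4/3, we report conservative estimation and inference on the causal risk" ratio.

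For the controlled risk curve r_C(s), the analysis is anchored at a central marker value s_cent where r_C is assumed equal to r_M. Above it, formula (21) bounds risk from above by r_M × B. Below it, formula (22) bounds risk from below by r_M / B. The point estimate of r_M is plugged into both, so (21) raises the estimated risk at high marker values, "and formula (22) pulls the observed risk" downwards at low ones. The section describes the flatter curve as the desired result.

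For the quantitative marker, point estimates and 95% CIs are to be plotted for the observed marginalized risk and controlled risk curves, "for the latter using the sensitivity analysis described in Section 15.1.1". No rule is given for the limits of the controlled risk curve. The sensitivity parameter there is set only "to some value above one".

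**The concern.** A conservative 95% CI should contain its target at least 95% of the time over the scenarios it claims to allow for. Here B stands for the largest plausible confounding, so weaker confounding is the ordinary case. RR_C then lies below RR_M × B, and raising the lower limit can leave RR_C beneath the interval.

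The curve has a related problem. Below s_cent, (22) gives only a floor for risk. Using that floor as the estimate lowers risk and so raises controlled VE at low antibody. That is cautious about whether the curve slopes, but favourable about how much protection exists at low marker values.

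These results are part of the robustness evidence for a controlled-VE correlate of protection. A reader who takes the word conservative at face value could understate how strong the correlate might be, or overstate VE at low titres.

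**Working it through.** **Inputs.** From Section 15.1.1: example RR_M = 0.40 with "confidence interval (CI) (0.14, 0.78). An E-value e(0,1) of 4.4 means that" confounding of that strength would explain it away; E-value 1.88 for the upper limit; both sensitivity parameters equal to 2. From Tables 4 and 10: at least 50 vaccine endpoint cases for Controlled VE.

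**The SAP's own figures reproduce.**
- B = (2 × 2)/(2 + 2 − 1) = 4/3, so ln B = 0.2877.
- E-values: (1 + √0.60)/0.40 = 4.44 and (1 + √0.22)/0.78 = 1.88.

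**The planned interval in the example.** 0.40 × 4/3 = 0.53; 0.14 × 4/3 = 0.187; 0.78 × 4/3 = 1.04. Result: 0.53 (0.19 to 1.04).

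**Coverage for RR_C.** Take log RR_M-hat as normal with standard error SE. From the example's interval width, SE = (ln 0.78 − ln 0.14)/3.92 = 0.438. (The interval is not symmetric about 0.40 on the log scale, so this SE is illustrative.) Write RR_C = RR_M × b, where b is the true bias, and d = (ln B − ln b)/SE. Coverage of (LL × B, UL × B) is Φ(1.96 − d) − Φ(−1.96 − d).
- b = B (assumed maximum): d = 0, coverage 95.0%.
- b = 1 (no confounding), SE 0.438: d = 0.657, coverage Φ(1.303) − Φ(−2.617) = 89.9%. A simulation of 1,000,000 draws gave 90.0%.

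**Coverage by number of cases, no confounding.** The SAP gives no SE, so assume cases split equally over tertiles and ignore two-phase sampling: SE² = 2/(n/3) = 6/n.

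| Vaccine cases | SE | Coverage of (LL × B, UL × B) |
|---|---|---|
| 25 | 0.490 | 91.0% |
| 50 | 0.346 | 86.8% |
| 100 | 0.245 | 78.3% |

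Coverage falls as cases accrue, because the shift by ln B stays fixed while the interval narrows.

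**The upper limit alone.** One-sided coverage of UL × B at SE 0.438 is 97.5% at maximum confounding and 99.6% with none.

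**Widening instead of shifting.** [LL, UL × B] = (0.14, 1.04) covers 97.1% at SE 0.438 both with no confounding and at the maximum, and slightly more in between.

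**The curve below s_cent.** With placebo risk fixed, dividing risk by B changes CVE to 1 − (1 − CVE)/B. At an illustrative B = 4/3, a point estimate of 70% becomes 1 − 0.30 × 0.75 = 77.5%. If the limits were scaled the same way, a lower CVE limit of 50% would become 62.5%, and 0% would become 25%.

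The curve's B is not fixed in the SAP. Assume RR_U = 2 between the 15th and 85th percentiles, a normal marker, and s_cent at the median. Then at the 15th percentile RR_U = √2 and B = 2/(2√2 − 1) = 1.09, taking 0% to 8.6%. At the 1st percentile B = 1.41, taking 0% to 29.2%.

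**The case against.** The section's heading announces upper-bound inference, and its main question is whether RR_C < 1. UL × B answers that validly, and the E-values do not use the shifted interval. The estimates are stated to be conditional on a presumed maximum of confounding, and under that scenario coverage is exactly 95%. The observed risk curve is plotted as well, so the reader can see the unadjusted result. The downward pull at low marker values is disclosed. The CVE(s) curve itself comes first from the nonparametric method of Section 15.1, which Section 16 prioritises if results conflict. All of this stands, and it limits the consequence. It does not give the lower limit the property its label claims, and nothing warns that the low-marker curve is favourable to the level of VE.

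Three stronger readings are tempting and are not supported:
- **Coverage is drastically low.** A figure such as 52% needs SE 0.15, which by 6/SE² is about 267 cases; 79% at SE 0.25 needs about 96. Neither SE is in the SAP. Still lower values (74% even at the example's SE) need maximum confounding in the opposite direction, making the marker look less protective than it is. The section is aimed at confounding that would explain protection away.
- **False correlates will be declared.** They will not on this account, because the upper limit is valid.
- **The plan raises the lower limit of controlled VE.** The rule of multiplying each limit is written for the risk ratio. For the curve only the point estimate is plugged in, and no CVE-limit formula is given.

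**Conclusion.** The concern holds in limited form and should be fixed. (LL × B, UL × B) is a 95% CI for the bound RR_M × B, wrongly described as a conservative 95% CI for RR_C; only its upper limit is conservative. With no unmeasured confounding, coverage is about 90% at the example's SE and about 87% at the 50-case minimum, falling further with more cases. These figures rest on log-normality and, for the case counts, on an equal split over tertiles without two-phase sampling.

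For the curve, it follows directly from (22) that the estimate below s_cent is conservative for slope but favourable to the level of controlled VE. That the lower CVE limit also rises is conditional on the limits being scaled like the estimate, which the SAP leaves open.

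**What to change.** - **Risk ratio.** Report [LL, UL × B] for RR_C. This follows from the plan's own one-directional setup and covers at least 95% for any bias from none up to B. Alternatively, report only the one-sided limit UL × B, and label (LL × B, UL × B) as a CI for the bound.
- **Confounding in either direction.** Use [LL/B, UL × B] (0.105 to 1.04 in the example) only if a bound for confounding in the opposite direction is also specified. Section 15.1.1 does not define one.
- **Controlled risk curve.** State the rule for its limits: at s ≥ s_cent multiply only the upper risk limit by B; at s < s_cent divide only the lower risk limit by B; leave the other limit unadjusted.
- **Wording.** State that the curve from (21) and (22) is conservative for the slope only, and not for the level of CVE(s) below s_cent.

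The cost is a change of SAP wording and about a line of code. The price is intervals that are wider on one side. The E-values need no change.

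### In SAP 15.1.1 the confounder's effect on the outcome shrinks with marker distance, so the anchored controlled-risk curve is not guaranteed conservative at the strength set for the 15th–85th percentile pair

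*Combined protocol and SAP*

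**What the plan says.** All of this is in SAP section 15.1.1.

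- RR_UD for a pair of marker values is the largest outcome risk ratio "comparing any two categories of the unmeasured confounders U, within either exposure group"; the two groups are those at the two marker values of the pair. The section adds that it "quantifies the importance of the unmeasured confounder U for the outcome", and assigns the imbalance of U between marker levels to RR_EU.
- The bias factor is B = RR_UD × RR_EU / (RR_UD + RR_EU − 1). Bound (20) states that the causal risk ratio is at most the marginalized risk ratio times B.
- The controlled-risk curve is anchored at s_cent, where marginalized risk equals overall vaccine-arm risk. Formulas (21) and (22) apply B between s_cent and each other marker value.
- On how B should vary between pairs, the section says "we note that it should have greater magnitude for a greater distance of", meaning the gap between the two marker values.
- For the quantitative marker, RR_UD and RR_EU share one value RR_U "that is specified log-linearly", with log RR_U = γ(s2 − s1). The parameter for the fixed pair is set "to some value above one", with no number. The pair is the 15th and 85th percentiles ("We anchor the sieve analysis by setting").
- For the tertiles both parameters are fixed at 2; the text reads "such that B(0,1) = 4/3, we report conservative estimation and inference on the causal", that is, on the contrast between the upper and lower tertile.

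**The concern.** The definition makes RR_UD the larger of two within-group effects, g(s1) and g(s2), where g(s) is the outcome risk ratio between levels of U at marker level s. If RR_UD is R at the 15th–85th pair, then g equals R at one of those percentiles. The anchored comparison that includes that percentile must then have RR_UD of at least R. The log-linear rule instead gives each anchored comparison a value set by its own shorter distance: √R on both sides if s_cent lies midway.

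B should indeed grow with distance, and growth in RR_EU alone achieves that. Shrinking RR_UD as well makes the correction too small around the anchor.

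At stake is the claim that the curve covers the presumed-maximum confounding. Part of an association produced wholly by a confounder of the strength set at the 15th–85th pair can remain in the plotted curve and be read as support for a controlled-risk correlate.

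**Working it through.** **Plan's own figure.** B(2, 2) = 2 × 2 / (2 + 2 − 1) = 4/3, as stated for the tertiles.

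**Shape of B as written.** With x = log RR_U, log B = 2x − log(2e^x − 1). Its derivative, (2e^x − 2)/(2e^x − 1), is zero at x = 0 and increasing. So log B is convex and about x² near the anchor. Two consequences follow:

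- The slope of the curve at s_cent is not corrected.
- B(15th, s_cent) × B(s_cent, 85th) is below the direct B(15th, 85th) whenever s_cent lies between the two.

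For R = 2 and a midway anchor, RR_U = √2 = 1.414 and B = 2/(2 × 1.414 − 1) = 1.0938. The product is 1.0938² = 1.197 against 1.333. The share of log B lost is 1 − ln 1.197/ln 1.333 = 38%.

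| Fraction of 15th–85th distance | RR_UD in plan | B in plan | B with RR_UD = 2 throughout |
|---|---|---|---|
| 0.10 | 1.07 | 1.0045 | 1.035 |
| 0.25 | 1.19 | 1.026 | 1.086 |
| 0.50 | 1.41 | 1.094 | 1.172 |
| 1.00 | 2.00 | 1.333 | 1.333 |

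For a normal marker anchored at the median, the plan's RR_UD reaches 2 only at z = 2 × 1.036 = 2.07, the 98th percentile.

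**Null-marker test.** Assumptions: S is normal with no causal effect; U is binary and multiplies risk by R at every s; P(U = 1 | s) = min(1, R^−t), where t is distance from the 15th percentile as a fraction of the 15th–85th distance. RR_EU then follows the plan's log-linear form between those percentiles. R = 2 is borrowed from the tertile analysis. True controlled risk is flat and equals overall risk, so the anchor assumption r_C(s_cent) = r_M(s_cent) holds exactly.

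- In units of risk with U = 0, r_M is 2 at the 15th percentile and 1.5 at the 85th. RR_M = 0.75, and bound (20) gives 0.75 × 4/3 = 1.00.
- Overall risk is 1.717, which puts s_cent at the 48th percentile, 0.479 of the way along the span.
- Formula (21) at the 85th: B = 1.101, and 1.5 × 1.101 = 1.652. This upper bound is 0.962 of the true risk, 4% too low.
- Formula (22) at the 15th: B = 1.087, and 2/1.087 = 1.840. This lower bound is 1.072 of the true risk, 7% too high.
- The 85th/15th ratio of the curve is 1.652/1.840 = 0.90, a false 10% fall. A simulation of 5 million gave 0.898.

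**Range over R, midway anchor.** The ratio is (2R − 1)/(2√R − 1)². It is below 1 for every R > 1, because (2√R − 1)² − (2R − 1) = 2(√R − 1)².

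| R | Plan | RR_UD held at R |
|---|---|---|
| 1.25 | 0.982 | 1.002 |
| 1.5 | 0.952 | 1.009 |
| 2 | 0.897 | 1.029 |
| 3 | 0.824 | 1.077 |
| 4 | 0.778 | 1.120 |

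**Weaker confounders, R = 2.** With prevalence of U at the 15th percentile at 90%, 75%, 60%, 50% and 30%, the plan's ratio is 0.91, 0.94, 0.975, 1.00 and 1.06. The 40th–60th percentile ratio stays below 1 even at 50% and 30% (0.969 and 0.984).

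**Anchor position, R = 2.** With s_cent at 25% to 75% of the span the ratio is 0.897 to 0.921. With s_cent exactly at the 15th or 85th percentile it is 1.00.

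**The case against.** The strongest defence is that the plan does not claim RR_UD = R for the plotted pairs. Section 15.1.1 allows the parameters to be context-specific, presents the log-linear form as one approach, and refers the details to a cited paper that is not available here. Only pairs that include s_cent are plotted, and a confounder with g(s) = exp(γ|s − s_cent|) reproduces the plan's RR_UD on all of them. So it would go too far to infer that RR_UD can never differ between pairs, or that the plan implies a confounder with no effect anywhere. The defence fails on one point: with a midway anchor that confounder has RR_UD = √R at the 15th–85th pair, not the R the user sets there.

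The size of the effect is also open to challenge, and this stands. The test confounder attains the bound: everyone at or below the 15th percentile has U = 1, which breaks positivity at that end. The fall survives just inside positivity (0.91 at 90% prevalence) but fades after that. A reader might infer that any marker explained wholly by a confounder of the set strength keeps a falling curve. For the 15th–85th contrast that is not so.

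Finally, a reader might infer that the plan's whole robustness assessment is undermined. It is not. The E-values and the tertile bound do not use this formula, no decision rule depends on the curve, and section 16 gives nonparametric results priority over contradictory Cox results where positivity is supported.

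**Conclusion.** The quantitative specification is wrong as written. It conflicts with the section's own definition of RR_UD, leaves the slope at s_cent uncorrected, and gives an anchored curve that is not guaranteed conservative at the strength set for the 15th–85th pair. The false 10% fall at R = 2 is a near-worst-case figure. It rests on an assumed R, a normal marker, a bound-attaining binary confounder and an anchor near the middle of the span. The defect is confined to one plotted curve per marker. It should be corrected before those curves are interpreted, but it does not call for more than that.

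**What to change.** In 15.1.1, hold RR_UD at a stated constant for all pairs, for example 2 as in the tertile analysis, and let only RR_EU(s1, s2) grow log-linearly with s2 − s1. State the value and use the same RR_UD for the tertile and quantitative analyses.

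With y = log RR_EU and RR_UD = R, the derivative of log B is (R − 1)/(R + e^y − 1), which decreases in y. So log B is concave in s2 − s1, and the product of B through the anchor is at least the direct B. In the test above the ratio becomes 0.75 × 1.1716² = 1.03 and both bounds hold.

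Making log B itself linear in distance may look like a simpler repair, but it is not enough. In the same test, formula (22) at the 15th percentile would still exceed the true risk by 1.5% at R = 2 and 5.7% at R = 4.

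The cost is one formula, one line of code and no new data. The conservative curve becomes somewhat flatter, most visibly near the centre.
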